1.2 Purpose

The purpose of this phase IV study is to identify innovative early imaging parameters as predictors of the long-term clinical response to brolucizumab in terms of fluid resolution in patients with wAMD with the purpose to evaluate their potential in supporting the treatment regimen choice (q12w or q8w).

2 Objectives and endpoints

Table 2-1 Objectives and related endpoints

Objective(s)	Endpoint(s)
Primary Objective The primary objective is to assess the predictive value of early anatomical parameters measured by multimodal imaging from Baseline to Week 16, in brolucizumab-treated participants with wAMD who present fluid resolution (i.e. absence of IRF and SRF) at Week 48 and have maintained the q12w treatment regimen up to Week 48 after the loading phase, defined also as fluid-free response (q12w fluid-free participants), compared with participants under a more frequent regimen and/or not fluid-free at Week 48.	Endpoint(s) for primary objective Early predictive factors of fluid-free response, which is defined as the absence of IRF and SRF (assessed by SD-OCT) at Week 48 in patients with a stable q12w treatment regimen up to Week 48 after the loading phase. The variables considered as potential predictive factors in the statistical model will be selected among the following qualitative and quantitative anatomical parameters: 
1. Basal CNV lesion type, as assessed by SD-OCT at Baseline and FA, ICGA and CFP at Screening2. Parameters assessed by OCTA at each visit from Baseline to Week 16, of which the main are presence/absence of branching vessels, peripheral anastomotic arcades, vascular loops and dark halo, and quantification of CNV flow size and vessel density3. Parameters assessed by SD-OCT at each visit from Baseline to Week 16, of which the main are presence/absence of sub-RPE fluid,

Objective(s)	Endpoint(s)
	subretinal hyperreflective material (SHRM), outer retinal tubulation, status of the External Limiting Membrane (ELM) and measurement of central retinal thickness (CRT) and PED volume.
Secondary Objective(s)	Endpoint(s) for secondary objective(s)

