2.1 Primary estimands

The primary clinical question of interest is: what are the early anatomical parameters detectable by multimodal imaging techniques used for the diagnosis and monitoring of patients with

wAMD that could predict the long-term clinical response to brolucizumab in terms of fluid resolution with a stable q12w treatment regimen?

The justification for targeting this clinical question is that we will capture the early anatomical parameters that could predict long-term fluid resolution in patients with wAMD treated with brolucizumab every 12 weeks, after the initial loading phase. Further details can be found in [Section 12](#).

The primary estimand is described by the following attributes:

1. Target population: male and female participants aged 50 years or older with untreated active subfoveal CNV secondary to wAMD in the study eye and with BCVA score greater than or equal to 23 letters at both Screening and Baseline. Further details about the population are provided in [Section 5](#).
2. Primary variables: predictive factors of fluid-free response, which is defined as the absence of IRF and SRF at Week 48 in patients with a stable q12w treatment regimen up to Week 48. Qualitative and quantitative anatomical parameters measured by FA, ICGA and CFP at Screening, and SD-OCT and OCTA at each visit from Baseline to Week 16 will be included as potential predictive factors in the statistical model.
3. Treatment of interest: The investigational treatment brolucizumab 6 mg taken for the entire study duration with the q8w or q12w regimen. The protocol defines the use of allowed concomitant medications for the target population, as well as medications which are prohibited. Further details about the investigational treatment are provided in [Section 6](#).
4. The summary measure is the odds ratio and/or beta estimates (fluid-free vs not fluid-free)

Detailed description of the primary estimand is provided in [Section 12.4](#).

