The best tree will be select considering jointly the two criteria: the Akaike Information Criterion (AIC) and the simultaneous significance levels (SLn). According to the minimum AIC principle

(Akaike, 1974), the honest tree should be the tree of the pruning sequence having the smallest AIC. This criterion is justified by the asymptotic equivalence of the minimum AIC model choice and leave-one-out cross validation. According to the SL approach, on the other hand, we should choose the smallest tree such that SL_n is larger than a pre-fixed value, e.g. 0.05 or 0.01. Since the AIC sequence decreases, reaches a minimum and then increases with a characteristic jump in the increment, while SL sequence can only decrease but up to a point at which the SL drops rather abruptly, we will choose the point in which both curves show a characteristic elbow (Ciampi et al., 1995).

Step 3: Construction of the amalgamation tree and selection of the RECPAM classification.

For a given statistical significance α level, the leaves of the honest tree will be amalgamated successively until any couple of leaves is dissimilar at the nominal α level. This results in a sequence of nested partitions of the set of leaves of the honest tree, forming the amalgamation tree. The partition corresponding to the minimum AIC, is selected: it defines the RECPAM classification (Ciampi et al., 1991).

A multivariable logistic regression will then be applied to study the association between q12w fluid-free patients at Week 48 with different imaging parameters using the above-mentioned variables and the cut-off selected by the RECPAM analysis. FA, ICGA and CFP variables included in the model are measured at Screening, while OCTA and SD-OCT variables included in the model are assessed at Screening (only SD-OCT), Baseline and Weeks 4, 8, 12 and 16. The variables selection will be based on an automated stepwise selection.

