Based on the study protocol, the primary endpoint should be analyzed according to Recursive Partitioning and Amalgamation (RECPAM) classification-tree analysis followed by multivariable logistic regression model. The RECPAM procedure was specified to evaluate interactions between imaging measurements assessed by OCT, OCTA, FA, ICGA and CFP and to identify distinct and homogeneous subgroups of participants in terms of q12w fluid-free participants at Week 48. This procedure should also have the aim to select the variables to be included in the multivariable logistic regression model and how to include them (for continuous, a threshold is identified during RECPAM). Based on data analyzed for the planned interim analysis, the image's grading of SD-OCT and mainly OCTA was affected by many ungradable values due to image's quality or due to pathology providing a great number of missing data that in RECPAM procedure cannot be managed. Moreover, the initial planned number of 263 enrolled patients wasn't reached, and the final number of 122 enrolled patient is too small for this type of the analysis. For these reasons, the RECPAM procedure will not be performed and in section 6.3.1 a different method to consider these variables in the multivariable logistic regression model and to choose them will be planned and explained. Moreover, the primary outcome will be considered as 'failure' also for patients who discontinued treatment during the study since for these patients the maintenance of a stable q12w regimen assigned at Week 16 up to Week 48 can not be observed and, thus, also these cases, will be considered as intercurrent event.

Moreover, in the primary analysis OCTA assessments planned in the study protocol will not be considered since based on interim analysis, it was observed that for these parameters most values will be missing.

| | |
|--|----------------------------------|
| | Statistical Analysis Plan |
| | Sponsor: Novartis |

Protocol: CRTH258AIT04

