2. STUDY OBJECTIVES AND ENDPOINTS

| OBJECTIVES | VARIABLES | ENDPOINTS |
|--|---|---|
| 
Primary objective(s):
 
The primary objective is to assess the predictive value of early anatomical parameters measured by multimodal imaging from Baseline to Week 16, in brolucizumab-treated participants with wAMD who present fluid resolution (i.e. absence of IRF and SRF) at Week 48 and have maintained the q12w treatment regimen up to Week 48 after the loading phase, defined also as fluid-free response (q12w fluid-free participants), compared with participants under a more frequent regimen and/or not fluid-free at Week 48.
 | 
To define the outcome of interest:
 
 • Intraretinal fluid (IRF) based on SD-OCT at Week 48 • Subretinal fluid (SRF) based on SD-OCT at Week 48 • Regimen assigned and followed during the study 
The following variable will be considered as predictive factors:
 
 1. Basal CNV lesion type (i.e., Type of predominant CNV lesion) 2. SD-OCT Parameters at each visit from Baseline to Week 16: 
 • Sub-retinal pigment epithelium (sub-RPE) fluid • Subretinal Hyperreflective Material (SHRM) • Outer Retinal Tubulation (ORT) • ELM integrity loss in center 1 mm • Type of PED • Center Subfield Thickness (CST) | 
Primary endpoint(s):
 
Early predictive factors of fluid-free response, which is defined as the absence of IRF and SRF (assessed by SD-OCT) at Week 48 in patients with a stable q12w treatment regimen up to Week 48 after the loading phase.
 
The variables considered as potential predictive factors in the statistical model will be selected among the following qualitative and quantitative anatomical parameters:
 
 1. Basal CNV lesion type (i.e., Type of predominant CNV lesion), as assessed by SD-OCT at Baseline and FA, ICGA and CFP at Screening 2. Parameters assessed by SD-OCT at each visit from Baseline to Week 16, of which the main are presence/absence of sub-RPE fluid, subretinal hyperreflective material (SHRM), outer retinal tubulation, status of the External Limiting Membrane (ELM) and measurement of central retinal thickness (CRT) and type of PED |

| | |
|--|----------------------------------|
| | Statistical Analysis Plan |
| | Sponsor: Novartis |
| | Protocol: CRTH258AIT04 |

| OBJECTIVES | VARIABLES | ENDPOINTS |
|--|---|--|

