NA=Not Applicable; CNV=Choroidal Neovascularization; UNG/P=Ungradable due to pathology; UNG/Q=Ungradable due to quality SHRM=Subretinal hyper reflective materia; ORT=Outer retinal tubulation; ELM=External Limiting Membrane; CST=Center Subfield Thickness; PED=Pigment Epithelial Detachment.

Of note, for each variable 'Missing' values can be present in case that images are collected but not graded by Central Reading Center (CRC) since they are collected by means of a not certificated instrument.

| | |
|--|----------------------------------|
| | Statistical Analysis Plan |
| | Sponsor: Novartis |
| | Protocol: CRTH258AIT04 |

Analysis methodology

Firstly, the proportion of patients with and without q12w fluid-free will be provided and then a descriptive summary table by q12w fluid-free and not q12w fluid-free will be provided for each variables described in table above.

A logistic models will be performed for each one of the variables listed above considering as outcome the patients' classification in q12w fluid-free and not q12w fluid-free.

Multivariable logistic model will be performed considering as outcome the patients' classification in q12w fluid-free and not q12w fluid-free and as covariates all the variables with $p<0.10$ in the previous analysis. Results of logistic models will be presented in terms of beta coefficient and standard error, Odds Ratio and relative 95% Confidence interval and p-value.

All these analyses will be performed on Safety population.

Data handling rules

In case of patients who dropped out at any time after baseline, the primary outcome cannot be evaluated since the patient status related to treatment regimen and presence of IRF o SRF at Week 48 are not observed. The dropped-out patients constitute intercurrent event and they will be considered a not q12w fluid-free at Week 48. Similarly, in case of patients who discontinued the treatment at any time after baseline, the primary outcome cannot be totally evaluated since the patient treatment regimen at q12w cannot be observed until Week 48. The patients who discontinued treatment constitute intercurrent event and they will be considered a not q12w fluid-free at Week 48.

Sensitivity of primary analysis

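### The primary objective is predictive value, but SAP 6.3.1 reports only association measures and a descriptive table, with no discrimination, calibration or correction for selecting variables on the same patients

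*SAP*

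**What the plan says.** SAP 2 gives the primary objective as "to assess the predictive value of early anatomical parameters measured by multimodal imaging from Baseline to Week 16", for the outcome of being fluid-free at Week 48 on a maintained q12w regimen. Protocol 1.2 adds that the parameters are to be judged for their potential to support the choice between q12w and q8w. Protocol 2.1 names the odds ratio and/or beta as the summary measure.

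In Protocol 12.4.2, a RECPAM tree was to find homogeneous subgroups. A logistic regression was then to be fitted "using the above-mentioned variables and the cut-off selected by the RECPAM analysis". SAP 1.1 drops RECPAM because of ungradable images and because 122 patients, not 263, were enrolled. It notes what that step would have delivered: "for continuous, a threshold is identified during RECPAM".

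The replacement in SAP 6.3.1 has four parts:

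- the proportion of patients in each outcome group;
- a table, described as "a descriptive summary table by q12w fluid-free and not q12w fluid-free will be provided for each variables described in table above";
- one logistic model per variable, then a multivariable model with every variable reaching p<0.10;
- a weighted refit with the same covariates, to address dropout.

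On reporting: "Results of logistic models will be presented in terms of beta coefficient and standard error, Odds Ratio and relative 95% Confidence interval and p-value". CST enters as percentage change from baseline, without a threshold. The other six candidates are categorical.

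**The concern.** An odds ratio measures association. It does not say how well the model separates patients who stay fluid-free on q12w from those who do not, or whether its predicted probabilities are right. Both matter if a marker is to inform the regimen choice.

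The SAP also chooses its covariates and estimates their effects on the same small sample. RECPAM had some protection against overfitting: permutation-based choice of splits, and pruning justified by an asymptotic link to leave-one-out cross-validation. The p<0.10 screen replaces its variable selection but not that protection, and not the cut-off or subgroup step. The report could therefore list predictors whose actual ability to predict is small or nil, with no figure that shows it.

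**Working it through.** **The plan's own figures.** Both documents size the trial on the responder proportion, using a Wald interval.

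- n = 1.96² × p(1−p) / 0.06². With p = 0.56: 3.8415 × 0.2464 / 0.0036 = 262.9, so 263, as stated.
- Full width at N = 122 and p = 0.50: 2 × 1.96 × √(0.25/122) = 17.74%, as stated in SAP 3.5.
- The limit of 12 covariates matches ten patients in the smaller outcome group per covariate: 263 × 0.44 / 10 = 11.6.

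These figures are correct, but none concerns prediction. By the same rule, N = 122 supports 122 × 0.44 / 10 = 5.4 to 122 × 0.50 / 10 = 6.1 covariates. The SAP 6.3.1 table has seven candidates with up to 18 coefficients: 2 for lesion type (three levels), 5 × 3 = 15 for the four-level factors, and 1 for CST.

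**What an odds ratio says about prediction.** Take a binary marker with prevalence m, overall response r, and response p1 with the marker and p0 without it. Then:

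- sensitivity = m·p1 / r
- specificity = (1−m)(1−p0) / (1−r)
- AUC = (sensitivity + specificity) / 2

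Marker prevalence is an assumption; the documents give none. Response is varied around the plan's range of 46% to 56%.

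| Odds ratio | m | r | Sensitivity | Specificity | AUC |
|---|---|---|---|---|---|
| 3 | 10% | 51% | 0.15 | 0.95 | 0.55 |
| 3 | 50% | 51% | 0.63 | 0.64 | 0.63 |
| 2.06 (just significant at N = 122) | 50% | 56% | 0.58 | 0.60 | 0.59 |
| 2.8 (80% power at N = 122) | 50% | 56% | 0.61 | 0.64 | 0.63 |

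For the third row, p1 = 0.648 and p0 = 0.472: sensitivity = 0.5 × 0.648 / 0.56 = 0.579, specificity = 0.5 × 0.528 / 0.44 = 0.600, and AUC = 0.589. By contrast, sensitivity and specificity both at 0.80 need an odds ratio of (0.8/0.2)² = 16. The same odds ratio can go with quite different prediction, and a significant one can go with little.

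**Optimism from selection.** The SAP rule was simulated with no marker related to outcome: N = 122, one three-level factor, five four-level factors and one continuous variable, screened at p<0.10. Level frequencies, independence of the markers and complete data are assumptions.

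- At least one variable passes the screen in about 55% of trials (54% to 57% over the settings tried). Seven independent tests at exactly 0.10 would give 1 − 0.9⁷ = 52%.
- At least one variable has a final-model p<0.05 in about 32% of trials.
- Where a model is selected, its apparent AUC averages about 0.65 (5th to 95th percentile 0.59 to 0.73). The true value is 0.50.

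**Precision if an AUC were reported.** By the Hanley–McNeil formula at N = 122, the 95% CI half-width is about 0.10 at an AUC of 0.60, 0.09 at 0.70 and 0.08 at 0.80. That is wide but informative.

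**The case against.** The strongest reply is that the output matches the pre-specified estimand. Protocol 2.1 names the odds ratio and/or beta, and both documents describe the estimand as identifying predictive factors. This stands: the SAP does not contradict its estimand, and the missing prediction measures predate it. The mismatch is with the objective and purpose.

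A reader might infer that no predictive value could be obtained for any marker. The documents do not support that. SAP 4.1 requires n and % for categorical data, and six of the seven candidates are categorical, so the crude proportion fluid-free per level follows from the planned table by division. Those values are not planned, carry no CI and are not corrected for selection. Nothing equivalent exists for CST or for the multivariable model.

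A reader might also take the 55% as the chance of declaring a false predictor. It is the chance of passing an entry screen. At the SAP's 0.05 level the figure is about 32%, and that is a multiplicity matter which reporting an AUC would not change. Nor is the apparent AUC of 0.65 a bias in a planned result, because no AUC is planned. It shows why an uncorrected one should not be added.

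Finally, the SAP openly discloses and explains the loss of RECPAM. Protocol 12.4.2 also does not say that subgroup response rates would be reported, so RECPAM should not be credited with a finished decision tool.

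**Conclusion.** The concern holds in this form: the objective asks for predictive value, and the primary analysis yields measures of association plus a descriptive table. There is no discrimination, no calibration and no correction for selecting variables on at most 122 patients. The number fitted may be lower, since ungradable lesion types and ungraded images count as missing. The lost cut-off step affects only CST change, as the other candidates already have levels.

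The simulated sizes rest on assumed level frequencies, independence and complete data; the conversions from odds ratio to AUC rest on assumed marker prevalence. The documents set no target level of prediction, so the plan cannot be said to miss one. Showing an AUC above 0.50 would not establish that a marker is good enough to guide regimen. Any AUC would also partly reflect investigator behaviour: the Week 16 regimen choice is part of the outcome, and it may rest on the same visit's SD-OCT findings (Protocol 8.3.6). No sample-size figure is wrong. The change should be made, but it is an addition to reporting and leaves the primary model as it is.

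**What to change.** Add to SAP 6.3.1:

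1. The AUC and calibration slope of the final multivariable model, with bootstrap optimism correction (for example 500 samples). Repeat the p<0.10 screen in every sample. Count a sample in which no variable is selected as an intercept-only model with AUC 0.50, and report how many such samples occur.
2. The proportion q12w fluid-free with 95% CI for each level of each categorical marker, and predicted probabilities with 95% CI across the observed range of CST percentage change. The latter replaces the lost threshold without choosing a new cut-off on the same data.
3. A statement that results at this sample size are exploratory associations unless externally validated, and that the AUC partly reflects the investigator's Week 16 regimen choice, which is part of the outcome.

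The cost is SAP wording and a short extra program, with no new data. The reported performance will be less favourable than an uncorrected figure.

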12.4.5 Sensitivity analyses for primary endpoint/estimand

A sensitivity analysis on the primary model will be performed using the LOCF approach in case of missing SD-OCT or OCTA evaluations between Week 4 and Week 16.

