12.4.7 Supportive analyses

To investigate the robustness of the primary analysis with respect to a potential selection bias due to dropouts, the following approach will be used: a weighted multivariable logistic regression will be applied to provide a robust inferential procedure for the analysis of predictors of patients' responses in presence of missingness. Since excluding participants because of missing values could introduce a selection bias, in order to restore the complete-case analysis to its

original sample representation, each complete participant will be weighted for the inverse of his/her missingness probability (evaluated by means of a logistic regression considering all baseline available covariates and the dropouts during the one-year period as response variables) (Höfler et al., 2005).

Further details will be provided in the Statistical Analysis Plan (SAP).

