For what concern the LOCF approach reported in the study protocol, this approach will be maintained for the predictors to be included in the analysis of the primary endpoint since the focus is on the first visits (from baseline to Week 16) and all enrolled patients should perform these visits independently of treatment regimen that will be followed by each patient. For the secondary endpoints, LOCF approach will not be applied because after Week 16 each patient will have different scheduled of visits based on treatment regimen. The LOCF approach can be considered only until Week 16 but (1) for OCTA the number of missing data will lead to most data imputed than the one observed, (2) for SD-OCT the approach is applied in the analysis of primary endpoint, (3) for BCVA the LOCF approach will be provided until Week 16, (4) for HAD and EQ-5D-5L questionnaires the LOCF approach will not be applied since only two assessments of these questionnaires are planned in the study.

As performed for interim analysis, all analysis will be conducted on Safety population since during the interim analysis, in which all enrolled patients were considered (see section 6.6 for further details), the FAS and Safety populations include the same set of patients since per definitions of the study protocol, the FAS considered all enrolled patients who completed the baseline visit and all of them are treated and consequently all of them belong to Safety population.

The evaluation of prevalence of anxiety and depression will be performed only based on HAD questionnaire and not based in terms of treatment that patients could have received for anxiety/depression.

The following additional analysis will be included:

- SD-OCT parameters at baseline and type of predominant lesion will be also analyzed according to BCVA groups and CST groups based on changes at Week 12 in patients who performed Week 16 and were still on treatment at this timepoint.
- A graphical representation of BCVA ETDRS score and CST by means of spaghetti plot will be provided.
- Analyses on CST and BCVA will be also performed on patients with BCVA ETDRS score lower than 69 letters at baseline.

| | |
|--|----------------------------------|
| | Statistical Analysis Plan |
| | Sponsor: Novartis |
| | Protocol: CRTH258AIT04 |

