- 1) To investigate the robustness of the primary analysis with respect to a potential selection bias due to dropouts, a weighted multivariable logistic model will be applied to provide a robust inferential procedure for the analysis of predictors of patients' responses in presence of missingness. Since excluding participants because of missing values could introduce a selection bias, in order to restore the complete-case analysis to its original sample representation, each complete participant will be weighted for the inverse of his/her missingness probability. Firstly, the missingness probability will be estimated by means of a multivariable logistic model in which the outcome variable will be the drop-out status (i.e., 1=patient drop-out; 0=patient who complete the study) and the covariates included will be the following baseline variables: age, sex, time from wAMD diagnosis in study eye to Informed consent (months), type of predominant CNV lesion, CST, BCVA EDTRS score. Secondly, the weighted multivariable logistic regression with the same covariate selected for the multivariable model

| | |
|--|----------------------------------|
| | Statistical Analysis Plan |
| | Sponsor: Novartis |
| | Protocol: CRTH258AIT04 |

previously described will be performed using the inverse missingness probability as weight. Of note, only patients with no missing data for each covariate included in the model can be considered in this analysis.

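### The dropout sensitivity analysis weights completers by 1/P(drop-out), but its stated aim needs 1/(1 − P(drop-out))

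*SAP*

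**What the plan says.** Under the sensitivity heading of SAP 6.3.1, the weighted analysis is built in two steps. First, a logistic model is fitted in which "the outcome variable will be the drop-out status (i.e., 1=patient drop-out; 0=patient who complete the study". Its covariates are "age, sex, time from wAMD diagnosis in study eye to Informed consent (months), type of predominant CNV lesion, CST, BCVA EDTRS score", and its fitted value is called the missingness probability. Second, "each complete participant will be weighted for the inverse of his/her missingness probability". The instruction is repeated for the outcome model, which "will be performed using the inverse missingness probability as weight". The stated purpose is "in order to restore the complete-case analysis to its original sample representation".

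Protocol 12.4.7 specifies the same construction, with drop-out over the year as the modelled response: "each complete participant will be weighted for the inverse of his/her missingness probability (evaluated by means of a logistic regression".

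Neither document mentions the probability of completing, or one minus the missingness probability. Neither says whether the weights are normalised or which variance estimator goes with the weighted fit.

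This is the only item listed under sensitivity of the primary analysis in SAP 6.3.1. Protocol 12.4.5 adds a separate check for missing early imaging ("A sensitivity analysis on the primary model will be performed using the LOCF approach"), and SAP 1.1 says of LOCF that "this approach will be maintained for the predictors to be included in the analysis of the primary endpoint".

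**The concern.** Inverse-probability weighting for drop-out lets each completer stand in for similar patients who left. The weight must therefore rise with the risk of leaving. The written weight falls with that risk, so completers least like the dropouts count most.

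The explicit 1/0 coding leaves no room to read the missingness probability as the probability of being observed. A programmer who follows the text builds the wrong weight, and one who silently corrects it departs from the SAP.

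The analysis exists to show whether drop-out has biased the primary result. As written it cannot do so. Agreement with the primary model would not reassure, and disagreement could come from the weight and be read as drop-out bias. If the raw weights are passed to a routine with model-based variance, the p-values would also be far too small.

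**Working it through.** The documents give no figure that depends on this weight, so there is none to reproduce. They also give no drop-out rate, so the rates below are assumptions. From the documents come the weight, the drop-out coding and the 122 enrolled patients (SAP 3.1).

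**1. Algebra.** Take a stratum of N patients with drop-out probability p. It yields N(1 − p) completers.

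- Weight 1/(1 − p): N(1 − p)/(1 − p) = N, which is the full sample.
- Weight 1/p: N(1 − p)/p, which falls as p rises.

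The direction of the error does not depend on the drop-out rate. It needs only that p varies between patients.

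**2. Two strata of 61 (total 122).** The high-risk stratum is 50% of the full sample. For 10% against 20% drop-out, completers number 61 × 0.90 = 54.9 and 61 × 0.80 = 48.8.

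- Unweighted share: 48.8/103.7 = 47.1%.
- With 1/p: 54.9/0.10 = 549 and 48.8/0.20 = 244, so 244/793 = 30.8%.
- With 1/(1 − p): 61/122 = 50.0%.

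| Drop-out, low / high stratum | Unweighted | 1/p (as written) | 1/(1 − p) |
|---|---|---|---|
| 5% / 10% | 48.6% | 32.1% | 50.0% |
| 10% / 20% | 47.1% | 30.8% | 50.0% |
| 10% / 30% | 43.8% | 20.6% | 50.0% |
| 20% / 40% | 42.9% | 27.3% | 50.0% |

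**3. One continuous covariate.** Let z be standard normal and logit p = a + bz. Completers weighted by 1/p have density proportional to φ(z)(1 − p)/p = φ(z)exp(−a − bz). That is a normal density with mean −b, whatever the drop-out rate. Simulation (1,000,000 patients per setting, drop-out 10%, 15% and 25%) agrees:

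| Weighting of completers | b = 0.3 | b = 0.5 | b = 0.8 |
|---|---|---|---|
| 1/p (as written), mean shift in SD | −0.30 | −0.50 | −0.80 |
| 1/(1 − p), mean shift in SD | 0.00 | 0.00 | 0.00 |

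Unweighted completers were off by −0.03 to −0.18 SD over the same grid. In 2,000 simulated trials of 122 with a fitted drop-out model (about 14.5% drop-out, b = 0.6), the written weight was further from the full sample than no weighting every time. The mean was −0.616 SD, against −0.085 unweighted, −0.003 with 1/(1 − p) and −0.003 in the full sample.

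**4. Precision.** Effective sample size is (Σw)²/Σw². With n = 122, 15% drop-out and about 104 completers, 1/p gives 96, 85 and 63 at b = 0.3, 0.5 and 0.8. The correct weight gives 102 to 104.

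**5. Odds ratio for a predictor.** 600,000 patients per setting, 15% drop-out, b = 0.8, binary predictor with log-odds ratio 0.6:

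| Scenario (assumed) | Full sample | Unweighted | 1/(1 − p) | 1/p |
|---|---|---|---|---|
| Driver changes predictor log-odds ratio by −0.4 per SD, correlation 0 | 1.79 | 1.87 | 1.79 | 2.45 |
| Same, correlation 0.4 | 1.58 | 1.65 | 1.58 | 2.07 |
| Driver main effect only, correlation 0.4 | 1.23 | 1.26 | 1.23 | 1.23 |
| Neither | 1.85 | 1.85 | 1.85 | 1.83 |

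In the first scenario, 1/p gives 2.02 at b = 0.3 and 2.17 at b = 0.5. Without an interaction, every weighting is within 0.03 of the full-sample value.

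**6. Scale and variance.** Even with a uniform 10% drop-out the scale is wrong: 122 × 0.90 = 109.8 completers, and 109.8/0.10 = 1,098, against 122 with 1/(1 − p). In 3,000 trials of n = 122 with a null predictor, 1/p weights rejected at 52–65% if left raw with model-based variance, 6–14% if normalised, and 5–7% with a sandwich variance. With 1/(1 − p) the rates were 6.5–8.8% raw and 4.8–5.2% with a sandwich variance.

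**The case against.** The wording cannot be defended, but several limits on its importance are fair.

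- **Different target.** The primary model counts dropouts as not q12w fluid-free, so drop-out leaves no primary outcome missing. A completer-only analysis answers a different question even with the right weight. Counting dropouts as failures (assuming about 50% response, 15% drop-out, b = 0.8), the primary-type / 1/(1 − p) / 1/p odds ratios were 1.74/1.80/2.43 with the interaction and zero correlation, and 1.70/1.83/1.81 with neither effect. This stands: the corrected analysis will also differ somewhat from the primary result, and where there is no interaction the choice of weight adds little.
- **Assumed effect modification.** The 2.45 needs an interaction of −0.4 per SD and the strongest drop-out driver tried. It is the worst case of an assumed grid.
- **Type I error.** The 52–65% arises only from raw weights with model-based variance, which the plan does not specify. Both documents describe the procedure as robust inference, which makes the naive reading less likely but does not name a variance. The figure supports stating the variance, not the point about direction.
- **Missing covariates.** The analysis keeps only patients with complete covariates, and SAP 1.1 reports many ungradable images. A drop-out weight does not address that. With 15–30% covariate missingness related to the same covariate (log-odds 0.3 to 0.8, assumed), completers weighted by 1/(1 − p) stay 0.05 to 0.22 SD off. The zero shift above therefore holds only when drop-out is the sole source of loss.
- **Supportive role.** The primary model, secondary endpoints, safety analyses and sample size are untouched.

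None of this makes 1/P(drop-out) the right weight for the stated aim.

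**Conclusion.** The point holds and should be fixed. The weight is wrong as written in both documents, and no other section corrects it. What is certain, whenever drop-out risk varies with the modelled covariates, is that the covariate mix moves further from the full sample than with no weighting, and that precision is lost. The size depends on the assumed rates. Bias in the odds ratios is conditional: it was material only where a drop-out driver modified the predictor effect, and negligible otherwise. If drop-out were unrelated to all six covariates, the true weights would be constant and the mix would not move, though their scale would still be wrong. The damage is confined to this one analysis, but it is the one meant to test robustness to drop-out.

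**What to change.** In SAP 6.3.1, replace the weighting instruction with:

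> Each participant who completes the study will be weighted by 1/(1 − estimated probability of drop-out), normalised to mean 1 (or stabilised). Confidence intervals and p-values will use a robust (sandwich) variance.

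Change the later sentence that describes the weight in the outcome model to match. Keep drop-out as the modelled event. Make the same correction in protocol 12.4.7, or list it in SAP 1.1 as a change from the protocol.

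It would help to add a sentence saying that this is a completer-only analysis and can differ from the composite primary result for that reason alone. A separate weighting for missing or ungradable covariates is optional; without it, the plan should not claim that the full sample is restored.

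The cost is two phrases in the SAP, one line in SAP 1.1 or a matching protocol edit, a one-line change to the weight and a robust-variance option in the code. No new data are needed.
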